This trial is for patients with resected pancreatic adenocarcinoma who have concluded adjuvant therapy or were deemed unable to receive adjuvant therapy with an elevated CA 19-9 or node positive or margin positive disease. CA 19-9 elevation is defined as two levels > the institutional upper limit of normal (ULN) taken at least 2 weeks apart. These levels should be measured after adjuvant therapy has concluded or upon the decision that adjuvant therapy will not be offered. Patients will be randomized to one of two arms. Subjects enrolled due to node + disease or R1 resection must be able to undergo randomization within 3 months of finishing adjuvant therapy or the decision that they are unable to take adjuvant therapy has completed. Group A, the treatment arm, will be started on CC-486. Group B, the control arm, will receive no additional therapy. In both arms, CA 19-9 will be followed and CT scans (or MRI, if clinically indicated) will be done every three months. When patients have visible disease recurrence on imaging, CC-486 will be stopped and both groups will start first-line chemotherapy.

Assuming the maximum accrual with a goal of 2-3 subjects accrued per month, we estimate enrollment duration of 24 months with an additional 12 months for follow-up with concurrent data analysis and manuscript preparation.

TOTAL SAMPLE SIZE:

Maximum 60 patients, with 30 patients in each of the two arms.

[figure not shown]
DRUG SUPPLIES:

For study participants, Celgene Corporation will provide CC-486

DOSING REGIMEN:

Treatment Arm	DRUG	DOSE	FREQUENCY	# of CYCLES	Route
Α	CC-486	300 mg total, three 100 mg tablets	Daily, Days 1- 21, Q28 Day cycles	12 cycles and then follow-up	Oral
В	Observation	N/A	N/A	12 cycles. Follow-up 1 will be collected 3 months after Cycle 10.	N/A

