5.3.2.2 Arm A for first 12 cycles

Arm A patients will be evaluated on Day 1 of every cycle with a physical examination, ECOG performance status, vital signs, weight, CBC with differential, research blood and serum chemistry and hepatic panel. Arm A patients will also complete an assessment of adverse events and reporting of current medications/procedures on Day 1 of every cycle.

Arm A patients will complete a CA 19-9, quality of life assessment and CT scan on Day 1 of every third cycle beginning at Cycle 4.

Arm A subjects will be evaluated for adverse events on Day 1 of each cycle with the NCI CTCAE v4.0 (http://ctep.info.nih.gov) used as a guide for the grading of severity. For Arm A patients, doses will be reduced for hematologic and other non-hematologic toxicities that can be attributed to the study drug. Dose adjustments are to be made according to the system showing the greatest degree of toxicity. When a dose reduction is required for Day 1 of any cycle, no dose re-escalation will be permitted for the duration of study treatment.

NOTE: Arm B patients will not be evaluated for adverse events as they do not receive the study agent.

Criteria to Initiate Treatment

In Arm A, a new course of treatment may begin on the scheduled Day 1 of a new cycle if:

- Absolute neutrophil count $\geq 1500/\text{mm}^3$
- Platelet count $\geq 100,000/\text{mm}^3$
- Serum creatinine levels < 2 mg/dL
- Serum bilirubin levels $\leq 1.5 \text{ mg/dL}$.
- AST (SGOT) and ALT (SGPT) \leq 2.5 x the institutional upper limit (ULN) of the normal range
- Any other drug-related adverse events that may have occurred must have resolved to < Grade 2 severity except grade 2 anorexia and any correctable metabolic abnormality.
- No evidence of visible disease recurrence on imaging (if indicated per Study Schedule, Section 2, to be done prior to cycles 4, 7, and 10)

If these conditions are not met on Day 1 of a new cycle, the subject will be evaluated weekly and a new cycle of treatment will not be initiated until the toxicity has resolved as described above utilizing the dose modifications as depicted below. If the study drug has to be held for > 28 days, study treatment will be discontinued.

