5.3.2.3 Arm B for the first 12 cycles

Arm B patients will ideally be evaluated (or at the very least contacted by the study team) on Day 1 of every third cycle beginning with Cycle 4.

Patients are permitted to see their local oncologist, and CA19-9 and lesion assessments may be completed outside of the recommended 3 month window (Cycles 4, 7, and 10) at their oncologist's discretion.

Arm B patients will follow a similar schedule as patients in Follow-up, except for a Quality of Life assessment that will be performed.

Correlative blood draw is optional for Arm B patients. If Arm B patients wish, they may have research bloods drawn for correlative studies.

Arm B patients who opt to have research blood collected will have it collected on Day 1 of every third cycle (cycle 4, 7 and 10).

Below is the list of information that must be obtained from Arm B patients.

- Any further therapy received (records to be obtained)
- Subjective response on therapy (records to be obtained)
- Any CA 19-9 drawn (records to be obtained)
- Any imaging (images to be obtained)

Arm B patients will complete a CA 19-9, quality of life assessment and CT scan (or alternate imaging, if clinically indicated) quarterly (ideally).

Arm B patients who are not evaluated in person may have the Quality of Life assessment completed over the [contact] Dose Modification

Table 5.3.1: Arm A: Dose Modification Recommendations for CC-486 Phase
--

Toxicity	Grade	CC-486
Febrile Neutropenia	Grade 3 or 4	Hold until resolved and neutrophils \geq 1500/mm ³
		Restart study drug at 200 mg (two tablets, 33% dose reduction).
		If the same Grade 3 or 4 event recurs (i.e., third occurrence) despite CC-486 dose reduction to 200 mg, as described above, permanently discontinue study
Leukopenia and/or Neutropenia	Grade 2-3Hold dose until recovery to Grade ≤ 1 or baseline.Resume study drug at prior dose	
	Grade 4	Hold until resolved to \leq Grade 1
		Restart study drug at 200 mg (two tablets, 33% dose reduction).
		If the same Grade 4 event recurs (i.e., third occurrence) despite CC-486 dose reduction to 200 mg, as described above, permanently discontinue study drug.
Thrombocytopenia	Grade 1* or 2	Hold treatment until resolution to normal values.
	Grade 3 or 4	Hold until resolved and platelet count ≥100,000/mm ³ Restart study drug at 200 mg (two tablets, 33% dose reduction)
Diarrhea (unresponsive to maximum medical	Grade 1 or 2	Consider administering symptomatic remedies and/or start prophylaxis.

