management)		No dose/schedule changes

Toxicity	Grade	CC-486	
	Grade 3 or 4	Hold until resolved to \leq Grade 1 Restart study drug at 200 mg (two tablets, 33% dose reduction).	
Nausea/Vomiting (unresponsive to maximum medical management)	Grade 1 or 2	Consider changing/adding antiemetic medication treatment No dose/schedule changes	
	Grade 3 or 4	Hold until resolved and neutrophils \geq 1000/mm3 Restart study drug at 200 mg (two tablets, 33% dose reduction).	

*Grade 1 thrombocytopenia: Platelet count < 100,000/mm³

Study drug should be stopped if grade 3 or 4 toxicity has occurred despite a dose reduction to 66% of original dose (200 mg of CC-486 in two 100 mg tablets).

If grade 3 or 4 toxicities require patients to stop treatment mid cycle, they can resume their cycle at the recommended decreased dose if the toxicities resolve to \leq Grade 1 within their 21 days of treatment (i.e. they would only continue treatment to complete their days 1-21 per the calendar, not to complete 21 days of taking the tablets). If their toxicities recover after their 21 days has completed, they will not take more tablets until they begin their next cycle.

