5.4 Discontinuation of Treatment: Arm A

In the absence of treatment delays due to adverse events, treatment with CC-486 may continue until one of the following criteria applies:

• Interruption of scheduled therapy for greater than four weeks,

- Intercurrent illness that prevents further administration of treatment,
- Adverse event(s) that, in the judgment of the Investigator, may cause severe or permanent harm or which rule out continuation of the treatment regimen
- For any grade 3 and 4 toxicity that recurs despite dose reduction
- Discontinuation of CC-486 for any reason,
- Treatment with other chemotherapeutic or investigational anti-neoplastic drugs,
- Subject decides to withdraw from the study,
- Suspected pregnancy or positive pregnancy, or
- General or specific changes in the subject's condition render the subject unacceptable for further treatment in the judgment of the investigator, or
- Disease recurrence on imaging, or
- Patient has completed one year of therapy with CC-486.

If the subject has visible disease recurrence on imaging or meets any of the aforementioned criteria for removal from study treatment, then the CC-486 or observation phase of this study will conclude and patient will enter the follow-up phase of the study, following the schedule of assessments as described in Section 5.4.2.9.

Mandatory research bloods and tumor biopsies will be obtained at the time of recurrence for both Arm A and Arm B subjects, per the method determined best per the investigator as outlined on the Study Calendar and in Section.

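### The CC-486 stopping rules contradict each other for recurrent grade 3/4 febrile neutropenia and grade 4 leukopenia/neutropenia, and for grade 3 leukopenia/neutropenia in a patient already at 200 mg

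*Combined protocol and SAP*

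**What the plan says.** Arm A starts at "300 mg total, three 100 mg tablets" (Section 1.1). Dose changes for toxicity are set out in three places.

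- **Table 5.3.1.** After grade 3 or 4 febrile neutropenia, or grade 4 leukopenia/neutropenia, the drug is held and then: "Restart study drug at 200 mg (two tablets, 33% dose reduction". Both rows end with permanent discontinuation if the same event comes back, qualified as "i.e., third occurrence) despite CC-486 dose reduction to 200 mg". For grade 2-3 leukopenia/neutropenia the drug is held until recovery, and the instruction is then: "Resume study drug at prior dose".
- **The two paragraphs below the table.** The first says: "Study drug should be stopped if grade 3 or 4 toxicity has occurred despite a dose reduction to 66% of original dose". The second concerns patients who stop mid-cycle for grade 3 or 4 toxicity and recover within the 21 dosing days: "they can resume their cycle at the recommended decreased dose".
- **Section 5.4.** The discontinuation criteria for Arm A include: "For any grade 3 and 4 toxicity that recurs despite dose reduction".

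Section 5.3.2.2 adds that, once a reduction is needed for Day 1 of a cycle, "no dose re-escalation will be permitted for the duration of study treatment".

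**The concern.** A dosing scheme should give one action for each combination of toxicity, grade, dose level and occurrence. Here an investigator who follows a specific table row may continue treatment where one who follows the general text must stop. CC-486 is handled as a cytotoxic drug (Section 5.1.1.3), the study runs at four centres (Section 5.1), and showing good tolerability is part of its stated goal (Section 1.1). Whether a patient is exposed again after a further grade 3/4 event should not depend on which paragraph a site consults.

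**Working it through.** **Dose levels.** 200/300 = 66.7% of the starting dose, a reduction of 100/300 = 33.3%. This matches the 33% in the table and the 66% in the text below it. The dose figures agree, and 200 mg is the only reduced level.

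**Passages side by side.**

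| Event | Dose at event | Table 5.3.1 | First paragraph below table | Section 5.4 |
|---|---|---|---|---|
| A. Febrile neutropenia grade 3/4, or leukopenia/neutropenia grade 4, first time | 300 mg | Hold, restart at 200 mg | Not triggered | Not triggered |
| B. Same event, second time | 200 mg | Stop by the recurrence condition; not yet by the bracketed count | Stop | Stop |
| C. Same event, third time | 200 mg | Stop | Should already have stopped | Should already have stopped |
| D. Leukopenia/neutropenia grade 3 | 200 mg | Hold, resume at 200 mg | Stop | Stop if it is a recurrence; unclear if new |
| E. A different grade 3/4 toxicity, such as nausea/vomiting after a reduction for diarrhea | 200 mg | Hold, restart at 200 mg | Stop | Unclear |

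**First contradiction (row B).** The reduction follows occurrence 1, so the first recurrence despite reduction is occurrence 1 + 1 = 2. The bracket says 3. The sentence therefore disagrees with its own row, and, read by the bracket, with the other two passages by one further event at 200 mg. Could an intervening event at 300 mg account for the count? The table has no step that re-treats at 300 mg after these events. Section 5.3.2.2 bars re-escalation after a Day 1 reduction, and no passage provides a return to 300 mg after a mid-cycle one.

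**Second contradiction (row D).** The prior dose is 200 mg, so the table re-treats at 200 mg. The paragraph below the table covers grade 3 as well as grade 4 and stops the drug. This conflict does not depend on how the bracketed count is read, and deleting the bracket would not remove it.

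**Two further ambiguities.** For mid-cycle grade 3 leukopenia/neutropenia at 300 mg, the second paragraph speaks of a decreased dose, but the table gives no decrease for that grade. In row E, the paragraph below the table is triggered by a toxicity having occurred at the reduced dose, while Section 5.4 requires one that recurs. The two may differ for a new toxicity.

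**Size.** Section 11.3.5 expects grade 3/4 toxicity in 15% of patients and aims to stay below 30%; Arm A has 30 patients.

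- At 15%: 0.15 x 30 = 4.5 patients with any grade 3/4 toxicity.
- At 30%: 0.30 x 30 = 9.

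Row B needs a second event of the same kind. Row D needs grade 3 leukopenia/neutropenia after an earlier reduction. Let s be the share of grade 3/4 patients who meet row B or D. The expected number is 4.5s or 9s. The documents give neither a recurrence rate nor a breakdown by toxicity, so s can lie anywhere from 0 to 1, and the expected number from 0 to 4.5 or from 0 to 9.

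**The case against.** The strongest reply is that the first contradiction hangs on one bracketed phrase in two of the five toxicity rows. Without it, the febrile neutropenia row agrees with the text below the table and with Section 5.4. The thrombocytopenia, diarrhea and nausea/vomiting rows carry no such phrase, and the general stop rule can be read as completing them. That is fair, but the phrase is in the current text and states a count, and row D remains without it.

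It can also be said that the table is titled as recommendations, that Section 5.3.2.2 tells sites to follow the system with the greatest toxicity, that Section 5.4 leaves room for investigator judgment, and that the monthly safety teleconferences (Section 10.5) would bring differences to light. These lower the risk. None sets an order of precedence, and the greatest-toxicity rule chooses between organ systems, not between two instructions for one event.

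Two stronger readings are tempting. A reader might infer that the mid-cycle paragraph flatly contradicts the table for grade 3 neutropenia. The documents do not support this: the decreased dose it mentions is the recommended one, which can refer back to the table and so cover only toxicities for which the table recommends a decrease. It is an ambiguity. A reader might also infer that the trial's reported tolerability results are distorted through discontinuation counts. No endpoint in Section 4.2 or 11.1 counts discontinuations, and the safety guideline in Section 11.3.5 counts grade 3/4 toxicities.

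**Conclusion.** The point holds for two contradictions: the second occurrence of grade 3/4 febrile neutropenia or grade 4 leukopenia/neutropenia, and grade 3 leukopenia/neutropenia at 200 mg. In each, the current text supports both stopping and re-treating. The mid-cycle wording and the handling of a new toxicity at 200 mg are ambiguities to settle at the same time.

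The size in patients is unknown. It would be wrong to infer that 4 to 5, or 9, patients will meet contradictory stopping rules: those figures count everyone in Arm A with any grade 3/4 toxicity and are ceilings on the expected number at the assumed rates. Nor do the documents show that sites will in fact diverge, only that the wording allows it. Because the primary comparison is as randomized (Section 11.2.1), its definition, the power and the type I error rate do not change. The case for correction rests on patient safety and consistent conduct.

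**What to change.** Reconcile the rows of Table 5.3.1, the two paragraphs below it and Section 5.4, so that each toxicity, grade, dose level and occurrence leads to one action, stated identically wherever it appears. In particular:

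- make the occurrence count in the febrile neutropenia and grade 4 leukopenia/neutropenia rows agree with the number of dose levels and with the general stop text;
- state one action for grade 3 leukopenia/neutropenia in a patient already at 200 mg;
- say whether the mid-cycle paragraph applies to grade 3 leukopenia/neutropenia;
- say whether a new grade 3/4 toxicity at 200 mg is treated like a recurrence.

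A sentence on which passage governs if they differ would guard against a repeat. The clinical team must decide which rule applies; this review takes no position. The cost is amendment wording, with no change to sample size or analysis.

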11.3.5 Safety Monitoring

Although the dose level is below the maximally tolerated dose, we will monitory the rates of grade 3/4 toxicity for individuals treated with CC-486. We would expect to observe grade 3/4 toxicities in 15% of patients. The goal is to ensure that the percentage of grade 3/4 toxicities remains below 30%. A Bayesian stopping guideline has been developed. The prior was chosen to be a Beta (1, 4), representing a 20% toxicity rate, which is at the high end of our expected value. The guidelines will recommend that the therapy be re-evaluated if the posterior probability of toxicity exceeding 30% is greater than 65%. Table 11.3.5.1 below summarizes the stopping guideline boundaries.

Table 11.3.5.1

Cohort size	Observed number of toxicities that trigger re-evaluation
6-9	4
10-12	5
13-15	6
16-18	7
19-21	8
22-24	9
25-27	10
28-31	11

The probability of triggering the stopping guidelines was assessed for a range of underlying toxicity rates based upon simulations with 5000 replicates (Table 11.3.5.2 below). In the expected range of toxicity, the probability of stopping early was less than 4.8%.

Table 11.3.5.2

True underlying toxicity rate	Probability of triggering stopping guideline boundaries
10%	1.2%
15%	4.8%
20%	14.1%
25%	32.2%
30%	54.1%
40%	89.6%
50%	99.1%

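### After Grade 3–4 thrombocytopenia, the mid-cycle restart paragraph allows 200 mg at Grade 1 counts below 100,000/mm3, where Table 5.3.1 requires a hold

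*Combined protocol and SAP*

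**What the plan says.** Four pieces of text bear on restarting CC-486 after severe thrombocytopenia.

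- **Mid-cycle paragraph, below Table 5.3.1.** It covers any Grade 3 or 4 toxicity that interrupts dosing within a cycle. Of these patients it says "they can resume their cycle at the recommended decreased dose if the toxicities resolve to" Grade 1 or lower within the 21 dosing days. Days missed are not made up. There is no separate condition for platelets.
- **Table 5.3.1, thrombocytopenia, Grade 3 or 4.** "Hold until resolved and platelet count" is at least 100,000/mm3, then restart at 200 mg.
- **Table 5.3.1, thrombocytopenia, Grade 1 or 2.** "Hold treatment until resolution to normal values".
- **Footnote to the Grade 1 entry.** "Grade 1 thrombocytopenia: Platelet count < 100,000" per mm3. No lower limit is given.

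Two passages in Section 5.3.2.2 come closest to settling the matter. One is the general dosing rule: "Dose adjustments are to be made according to the system showing the greatest degree of toxicity". The other is the list of criteria for starting a new cycle, which includes platelets of at least 100,000/mm3.

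**The concern.** A patient recovering from a Grade 3–4 platelet count will usually pass through Grade 1 before reaching 100,000/mm3. In that interval an investigator who follows the mid-cycle paragraph may dose, and one who follows the table must hold. Both can point to protocol text, and the study runs at four institutions.

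The restart count matters to the patient because a further severe event ends treatment. Section 5.4 lists this among the reasons to discontinue: "For any grade 3 and 4 toxicity that recurs despite dose reduction". Restarting too early and waiting too long both carry a cost, so the protocol should state one threshold.

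**Working it through.** There is no planned figure to reproduce. The check is a comparison of the rules, followed by simple arithmetic on scale.

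**Step 1: the rules side by side.** Take a patient stopped mid-cycle at 300 mg by Grade 3–4 thrombocytopenia, still within days 1–21.

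| Platelets now | Mid-cycle paragraph | Grade 3–4 row | Grade 1–2 row |
|---|---|---|---|
| Still Grade 2 or worse | No restart | Hold | Hold (at Grade 2) |
| Grade 1, below 100,000/mm3 | May restart at 200 mg | Hold | Hold |
| 100,000/mm3 or above | May restart at 200 mg | Restart at 200 mg | Not triggered, by the footnote's limit |

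Only the middle line conflicts.

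**Step 2: does the footnote's purpose matter?** It can be read as describing Grade 1, or as limiting which Grade 1 counts trigger the hold. Under either reading, a Grade 1 count below 100,000/mm3 is a hold in the table and a permitted restart in the paragraph. The lower end of Grade 1 is not in the documents, so the width of the disputed range cannot be stated.

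**Step 3: does other text decide?** The rule in Section 5.3.2.2 on the greatest degree of toxicity chooses between organ systems; here there is one system and two restart conditions. The 100,000/mm3 criterion in the same section applies to Day 1 of a new cycle. Section 5.3.2.5 deals with missed doses only. None ranks the paragraph against the table.

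**Step 4: who can be affected?**
- Any Grade 3/4 toxicity: Section 11.3.5 states "We would expect to observe grade 3/4 toxicities in 15% of patients". With 30 patients in Arm A, 30 × 0.15 = 4.5; at the 30% limit in that section, 30 × 0.30 = 9. These counts cover all severe toxicities, so they do not measure this problem.
- Mid-cycle thrombocytopenia is a subset of unknown size. The sentence that begins "Arm A patients will be evaluated on Day 1 of every cycle with a physical examination" also sets the blood count for Day 1, and the schedule in Section 2.1 agrees. The conflict therefore needs an unscheduled count that shows Grade 3–4, then another before day 21 that shows Grade 1 but is still under 100,000/mm3. A low count found on Day 1 of a new cycle falls under the new-cycle criterion, which is clear.
- A patient already reduced to 200 mg who has a Grade 3–4 toxicity stops the drug under the text below the table, so the question arises only at the first reduction from 300 mg.

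**Step 5: what is at stake per day?** Each disputed day is one 200 mg dose. The planned full dose is 300 mg × 21 = 6,300 mg per cycle, and 200 / 6,300 = 3.2%. The documents give no basis for assuming how many days would be disputed.

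**The case against.** The strongest reply is that both texts can be obeyed together. The paragraph only permits a restart, takes its dose from the table, and is mainly concerned with whether missed days are made up. The table's rows are instructions to hold. Several rows add a laboratory condition to recovery, which suggests that Grade 1 is a general floor and the row a further requirement. The value 100,000/mm3 also appears in the new-cycle criteria and in inclusion criterion 12 (Section 5.2.1). A site that holds breaches nothing.

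This is probably what was intended, and it keeps the point minor. It does not remove it. The paragraph is the only text written for mid-cycle restart, and it states its own recovery threshold, the same one as in the Grade 3–4 diarrhea and Grade 4 neutropenia rows. An investigator could reasonably take it as the governing rule, and the table is headed as recommendations. The intended answer has to be inferred.

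A reader might go further and infer that every mid-cycle restart at Grade 1 or lower contradicts the table. It does not, because Grade 1 or lower includes full recovery, where the rules agree. A reader might also count as errors the undefined normal values in the Grade 1–2 row, or the neutrophil condition in the Grade 3–4 nausea/vomiting row. The documents show no effect of either on dosing, and removing the neutrophil condition would take away a safety requirement. Neither belongs in this point.

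**Conclusion.** The conflict stands, as a minor one. Followed literally, the mid-cycle paragraph permits a 200 mg dose at a Grade 1 platelet count below 100,000/mm3 that Table 5.3.1 says to withhold. The rules agree from 100,000/mm3 upward.

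The number of patients affected is unknown and probably very small. That judgement assumes that few counts are taken outside the Day 1 schedule; more frequent unscheduled testing would enlarge the group. The conclusion also takes from the footnote that Grade 1 includes counts below 100,000/mm3.

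A reader might infer that earlier restart leads to more recurrent toxicity or more discontinuations, or that the trial's inference is affected. The documents give no recurrence rate, so the first cannot be claimed. The second does not follow: power, alpha and the primary analysis, which compares all patients as randomized, are unchanged.

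**What to change.** Add one clause to the mid-cycle paragraph, after the Grade 1 condition: *and the toxicity-specific restart condition in Table 5.3.1 is met (for thrombocytopenia, platelets at least 100,000/mm3)*.

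This adopts the threshold already in the Grade 3–4 row and leaves the rest of the table alone. The cost is an amendment of wording. Where a site now uses the looser reading, restart after thrombocytopenia becomes stricter, so a few patients may miss some 200 mg doses, and these are lost because missed days are not made up.
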